### 8.2.7. Pregnancy

A serum or urine pregnancy test will be administered to all female participants of childbearing potential. A negative serum pregnancy test at the Screening Visit and a negative urine pregnancy test at Day 1 are required in order to be considered eligible to continue in the study.

Pregnancy data from female participants and female spouses/partners of male participants will be collected from the first dose of study intervention and at the time points specified in the SoA (Section 1.3). Any female participant who becomes pregnant during the study will be

discontinued from the study intervention and withdrawn from the study. If a pregnancy is reported, the Investigator must immediately inform Alexion within 24 hours of awareness of the pregnancy and follow the procedures outlined in Section 10.5.3.

# 8.2.8. Participant Safety Card

Before the first dose of the study intervention, a Participant Safety Card will be dispensed during the Day 1 Visit. The safety card is provided to increase participant awareness of the risk of meningococcal infections, promote rapid recognition and disclosure of any potential signs or symptoms of infection experienced during the course of the study, and to inform participants of what actions must be taken if they are experiencing signs or symptoms of an infection.

At each visit/contact throughout the study, the study staff will ensure that the participant has the Participant Safety Card and review the content of the safety card with the participant. Participants are required to carry the safety card until 30 days after the final dose of study intervention.

# 8.3. Adverse Events and Serious Adverse Events

The definitions of AEs and SAEs can be found in Section 10.3.

All AEs will be reported to the Investigator or qualified designee by the participant (or, when appropriate, by a caregiver, surrogate, or the participant's legally authorized representative).

The Investigator and any qualified designees are responsible for detecting, documenting, and recording events that meet the definition of an AE or SAE and remain responsible for following up AEs that are serious, considered related to the study intervention or study procedures, or that caused the participant to discontinue the study intervention (see Section 7).

Procedures for recording, evaluating, follow-up, and reporting AEs and SAEs are outlined in Section 10.3.

# 8.3.1. Time Period and Frequency for Collecting AE and SAE Information

All AEs and SAEs will be collected from the signing of the ICF at the time points specified in the SoA (Section 1.3).

All SAEs will be recorded and reported to Alexion immediately and under no circumstance should this exceed 24 hours, as indicated in Section 10.3. The Investigator will submit any updated SAE data to Alexion within 24 hours of the date the investigational site became aware of the event.

Investigators are not obligated to actively seek AE or SAE data after conclusion of the study participation. However, if the Investigator learns of any SAE, including a death, at any time after a participant has been discharged from the study, and he/she considers the event to be reasonably related to the study intervention or study participation, the Investigator must promptly notify Alexion.

# 8.3.2. Method of Detecting AEs and SAEs

The method of recording, evaluating, and assessing causality of AEs and SAEs and the procedures for completing and transmitting SAE reports are provided in Section 10.3.

Care will be taken not to introduce bias when detecting AEs and/or SAEs. Open-ended and nonleading verbal questioning of the participant is the preferred method to inquire about AE occurrences.

# 8.3.3. Follow-up of AEs and SAEs

After the initial AE/SAE report, the Investigator is required to proactively follow-up on each participant at subsequent visits/contacts. All SAEs will be followed up until resolution, stabilization, the event is otherwise explained, or the participant is lost to follow-up (as defined in Section 7.3). Further information on follow-up procedures is provided in Section 10.3.

### 8.3.4. Regulatory Reporting Requirements for SAEs

- Prompt notification of an SAE by the Investigator to Alexion is essential so that legal obligations and ethical responsibilities towards the safety of participants and the safety of a study intervention under clinical investigation are met.
- Alexion has a legal responsibility to notify both the local regulatory authority and other regulatory agencies about the safety of a study intervention under clinical investigation. Alexion will comply with country-specific regulatory requirements relating to safety reporting to the regulatory authority, IRBs/IECs, and Investigators.
- Alexion or designee is required to submit individual SUSAR reports (defined in Section 10.3.2) in the format of MedWatch 3500 or CIOMS I Form to health authorities and Investigators as required. Forms submitted to Investigators will be blinded to treatment assignment. In limited circumstances, the blind may be broken in the case of urgent safety issues that could compromise participant safety.
- An Investigator who receives an Investigator safety report describing an SAE or other specific safety information (eg, summary or listing of SAEs) from Alexion will review and then file it along with the IB and will notify the IRB/IEC, if appropriate according to local requirements.
- Under the EU CTR 536/2014, events other than SAEs (eg, unexpected events) that may impact the benefit-risk balance should be reported. See definitions in Section 10.3.5.

### 8.3.5. Medication Error, Drug Abuse, and Drug Misuse

#### 8.3.5.1. Timelines

If an event of medication error, drug abuse, or drug misuse occurs during the study, then the Investigator or other site personnel informs the appropriate Alexion or designee immediately but no later than 24 hours of when they become aware of it.

The full definitions and examples of medication error, drug abuse, and drug misuse can be found in Section 10.4.

### 8.3.5.2. Medication Error

For the purposes of this clinical study a medication error is an unintended failure or mistake in the treatment process for an investigational medicinal product (IMP) or Alexion AxMP that either causes harm to the participant or has the potential to cause harm to the participant.

#### 8.3.5.3. Drug Abuse

Drug abuse is the persistent or sporadic intentional, non-therapeutic excessive use of IMP or Alexion AxMP for a perceived reward or desired non-therapeutic effect.

### 8.3.5.4. Drug Misuse

Drug misuse is the intentional and inappropriate use of IMP or Alexion AxMP for medicinal purposes outside of the authorized product information, or for unauthorized IMPs or Alexion AxMPs, outside the intended use as specified in the protocol and includes deliberate administration of the product by the wrong route.

# 8.4. Treatment of Overdose

For this study, any dose of IMP or Alexion AxMP greater than that specified in the protocol will be considered an overdose. Any blinded dose greater than that specified in the protocol will be considered a suspected overdose.

Alexion does not recommend specific treatment for an overdose. General supportive measures are recommended.

Overdoses are medication errors that are not considered AEs unless there is an untoward medical occurrence resulting from the overdose.

In the event of an overdose or suspected overdose, the Investigator should:

- 1. Capture and forward the event, with or without associated AEs, to Alexion Global Patient Safety via email or facsimile ([contact] or [name]) using the Alexion Clinical Study Overdose Report Form within 24 hours of awareness.
- 2. Contact the Medical Monitor immediately.
- 3. Evaluate the participant to determine, in consultation with the Medical Monitor, if possible.
- 4. Closely monitor the participant for any AE/SAE and laboratory abnormalities.
- 5. Obtain a plasma sample for PK analysis if requested by the Medical Monitor (determined on a case-by-case basis).
- 6. For unblinded participants, document the quantity of the excess dose as well as the duration of the overdose in the eCRF.

Decisions regarding dose interruptions or modifications will be made by the Investigator in consultation with the Medical Monitor based on the clinical evaluation of the participant.

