#### Events Meeting the AE Definition

- Any abnormal laboratory test results (hematology, clinical chemistry, or urinalysis) or other safety assessments (eg, ECG, radiological scans, vital signs measurements), including those that worsen from baseline, considered clinically significant in the medical and scientific judgment of the Investigator (ie, not related to progression of underlying disease).
- Exacerbation of a chronic or intermittent pre-existing condition including either an increase in frequency and/or intensity of the condition.
- New conditions detected or diagnosed after study intervention administration even though it may have been present before the start of the study.
- Signs, symptoms, or the clinical sequelae of a suspected drug-drug interaction.
- Signs, symptoms, or the clinical sequelae of a suspected overdose of either study intervention or a concomitant medication. Overdose per se will not be reported as an AE/SAE unless it is an intentional overdose taken with possible suicidal/self-harming intent. Such overdoses should be reported regardless of sequelae.

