#### **Events Not Meeting the AE Definition**

- Medical or surgical procedure (eg, endoscopy, appendectomy): The condition that leads to the procedure is the AE. Situations in which an untoward medical occurrence did not occur (eg, hospitalization for elective surgery if planned before signing the ICF, admissions for social reasons or for convenience).
- Anticipated day-to-day fluctuations of pre-existing disease(s) or condition(s) present or detected at the start of the study that do not worsen.
- A medication error (including intentional misuse, abuse, and overdose of the product) or use other than what is defined in the protocol is not considered an AE unless there is an untoward medical occurrence as a result of a medication error.
- Cases of pregnancy that occur during maternal or paternal exposure to study intervention are to be reported within 24 hours of Investigator/site awareness. Data on fetal outcome and breastfeeding will be collected for regulatory reporting and safety evaluation.

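### The protocol gives conflicting rules on whether an intentional overdose with possible self-harm intent and no sequelae is an adverse event, so its place in the TEAE and TESAE tables depends on which section the site follows

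*Protocol*

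**What the plan says.** Four places in the protocol bear on whether an overdose is an AE.

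- Section 8.4 (Treatment of Overdose): "Overdoses are medication errors that are not considered AEs unless there is an untoward medical occurrence resulting from the overdose". This covers every overdose, whatever the intent.
- Section 10.3.1, list of events meeting the AE definition: "Overdose per se will not be reported as an AE/SAE unless it is an intentional overdose taken with possible suicidal/self-harming intent". The next sentence adds: "Such overdoses should be reported regardless of sequelae".
- Section 10.3.1, list of events not meeting the AE definition: the entry opens "A medication error (including intentional misuse, abuse, and overdose of the product" and rules that such an event "is not considered an AE unless there is an untoward medical occurrence as a result of a medication error". It has no self-harm exception.
- Section 8.3.5.2, repeated in Section 10.4: "a medication error is an unintended failure or mistake in the treatment process".

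Section 10.3.2 adds that an event outside the AE definition cannot be an SAE, even when a seriousness criterion is met. Section 9.4.7.1 of the protocol and Section 5.6.1.2 of the SAP build the adverse event tables from TEAEs and TESAEs. The SAP has no separate overdose table.

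**The concern.** The incidence of TEAEs and TESAEs is a stated safety endpoint, and suicidal ideation and behavior are actively monitored under Section 8.2.6. A deliberate overdose with possible self-harm intent is the kind of event a safety reviewer would expect to find in those tables. Two of the three rules that classify it would keep it out when no harm results.

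More than a table row depends on the classification. Section 10.3.3 requires an investigator causality and intensity assessment for AEs, and the SUSAR definition in Section 10.3.2 presupposes a serious event. An overdose not classed as an AE bypasses these steps. The terminology adds to the problem: Section 8.4 calls every overdose a medication error, and the second list in Section 10.3.1 puts intentional acts under that term, while the protocol's own definition limits it to unintended acts.

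**Working it through.** No arithmetic applies; the point rests on wording. The check is to run each kind of overdose through the three classifying rules.

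| Event | Section 8.4 | 10.3.1, events meeting | 10.3.1, events not meeting |
|---|---|---|---|
| Any overdose followed by an untoward medical occurrence | AE | AE (signs, symptoms or sequelae) | AE |
| Accidental overdose, nothing follows | Not an AE | Not an AE | Not an AE |
| Intentional overdose, no self-harm intent, nothing follows | Not an AE | Not an AE | Not an AE |
| Intentional overdose, possible self-harm intent, nothing follows | Not an AE | Reported as AE/SAE | Not an AE |

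The rules agree in the first three rows and conflict only in the last.

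Following that row through:

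1. A site applying Section 8.4, or the second list in Section 10.3.1, records no AE.
2. Under Section 10.3.2 the event then cannot be an SAE.
3. The TEAE and TESAE summaries in SAP Section 5.6.1.2 draw on recorded AEs, so the event appears in neither.
4. A site applying the first list in Section 10.3.1 records an AE, and the event is eligible for both.

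Other routes by which the event is captured:

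- Section 8.4, item 1, requires an overdose report form within 24 hours, with or without an associated AE.
- The C-SSRS is scheduled at each post-baseline clinic visit in the Primary Evaluation Period and at the in-clinic treatment visits of the later periods. SAP Section 5.6.1.3.4 summarizes suicidal behavior, and separately self-injurious behavior without suicidal intent, by treatment group.

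Both routes work, but neither feeds the AE tables.

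On terminology, Section 8.4 and the second list place intentional overdose under medication error, which Sections 8.3.5.2 and 10.4 define as unintended. Section 10.4 also excludes accidental overdose from medication error reporting and sends it to Section 8.4. Section 8.4 then calls it a medication error again.

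**The case against.** The best defense is that a specific exception qualifies a general rule. Section 8.3 sends the reader to Section 10.3 for AE definitions, so Section 8.4 is not the defining text. Within Section 10.3.1 the first list states the general rule on overdose and then one explicit exception; the second list can be read as restating the general rule. That reading is reasonable and probably intended. But no section states it, Section 8.4 does not point to the exception, and the second list names intentional acts without reserving the self-harm case. Section 8.4 is also where a site would naturally look when an overdose occurs.

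An investigator might also treat the self-harm act itself as the untoward occurrence and record it. That would close the gap in practice. However, Section 8.4 and the second list look for an occurrence resulting from the overdose or error, so the text does not secure it.

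The back-up capture stands as an objection to any wider claim. A reader might infer that self-harm overdoses in general could vanish from the study; they would not. If any untoward occurrence follows, all the rules agree on an AE. If none follows, the overdose form still reaches the sponsor and the C-SSRS should show the behavior.

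A reader might also take item 6 of Section 8.4 ("For unblinded participants, document the quantity of the excess dose as well as the duration of the overdose in the eCRF") to mean that the eCRF holds no overdose size for blinded participants. The documents do not support that. Section 6.4 requires returned tablets to be counted and deviations from the prescribed regimen to be entered in the eCRF for all participants, and SAP Section 5.6.1.1 computes tablets received from eCRF counts. The overdose form applies to blinded participants too.

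**Conclusion.** The contradiction is real, both between Sections 8.4 and 10.3.1 and within Section 10.3.1. It affects one class of event: an intentional overdose with possible suicidal or self-harming intent and no sequelae. For that class, inclusion in the TEAE and TESAE tables depends on which text the site follows.

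Its size cannot be put in numbers. The documents give no overdose or self-harm rate. Stating one event as a share of a treatment group would show only the weight of any single event, not how likely this one is. The efficacy analyses are untouched.

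The conclusion assumes that sites apply the wording as written and that no training material or eCRF guideline outside these documents settles the matter. It is a modest point, worth correcting because it concerns safety capture and the correction is nearly free. It also remains relevant after the decision to terminate: Section 1.2 of the SAP Addendum keeps all planned safety analyses, using data collected to the end of the study.

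**What to change.** Reconcile the three texts to one reporting rule.

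- Carry the exception already in the first list of Section 10.3.1 into Section 8.4 and into the second list, or add an explicit cross-reference to it in both places.
- In Section 8.4 and the second list, use medication error only for unintended events, in line with Sections 8.3.5.2 and 10.4. Name intentional overdose, misuse and abuse separately.

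This creates no new reporting rule and adds no visit, procedure or data field; it costs a few lines in two protocol sections. Revised wording cannot reclassify events already recorded. Before the final safety tables are produced, it would also help to compare the overdose report forms and C-SSRS behavior entries with the AE listing, to see whether any event fell into the gap. That is one reconciliation of data already held. Item 6 of Section 8.4 needs no change on this account.

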# 8.5. Pharmacokinetics

- Biomatrix samples (eg, plasma, serum, or whole blood) will be collected for measurement of concentrations of ALXN2050 as specified in the SoA (Section 1.3).
- Instructions for the collection and handling of biological samples will be provided by Alexion. The actual date and time (24-hour clock time) of each sample will be recorded.
- Samples will be used to evaluate the PK of ALXN2050.
- PK data may be used for research to develop methods, assays for prognosis, diagnostics, and/or treatment monitoring related to gMG, pathways associated with the disease state, and/or mechanism of action of ALXN2050.
- Study intervention concentration information that would unblind the study will not be reported to investigational sites or blinded personnel until the study has been unblinded.

# 8.6. Pharmacodynamics

- Biomatrix samples (eg, plasma, serum, and whole blood) will be collected for measurement of AP activity and Bb as specified in the SoA (Section 1.3).
- Instructions for the collection and handling of biological samples will be provided by Alexion. The actual date and time (24-hour clock time) of each sample will be recorded.
- Samples will be used to evaluate the PD of ALXN2050. Samples collected for analyses of ALXN2050 (plasma, serum, whole blood) concentration may also be used to evaluate safety or efficacy aspects related to concerns arising during or after the study.

# 8.7. Genetics

Genetics are not evaluated in this study.

# 8.8. Biomarkers

- Samples will be collected for analyses that may include but are not limited to evaluation of complement components (eg, FD, C3, CP activity), anti-AChR antibody, and other nongenetic exploratory biomarkers (eg, anti-MuSK antibodies, anti-low density lipoprotein receptor-related protein 4 [LRP4] antibodies, matrix metalloproteinase 10 [MMP-10], interleukin 6 [IL-6]) in adult participants with gMG.
- Blood samples for biomarker research will be collected from all participants in this study.
- Additional details regarding how biomarkers will be collected and analyzed are provided in Section 10.6.

# 8.9. Immunogenicity Assessments

Immunogenicity is not applicable in this study.

# 8.10. Health Economics Data and/or Medical Resource Utilization

Medical resource utilization and/or health economics data will not be collected during this study.

# 8.11. Other Assessments and Procedures

#### 8.11.1. Informed Consent

Participants or their legally authorized representative must be consented per the informed consent process outlined in Section 10.1.3.

#### 8.11.2. Demographics

A review of demographic parameters, including age, gender, race, and ethnicity, will be performed if allowed per country-specific regulations.

#### 8.11.3. Inclusion and Exclusion Criteria

All inclusion (Section 5.1) and exclusion (Section 5.2) criteria must be reviewed by the Investigator or qualified designee to ensure the participant qualifies for study participation.

### 8.11.4. Medical History and MG History

The participant's MG history and relevant medical history, including prior and concomitant conditions/disorders, treatment history, substance usage, and history of medical conditions and surgeries will be evaluated by the Investigator and documented in the source documents and eCRF.

Myasthenia gravis history will include diagnosis date; initial MG clinical presentation (ocular myasthenia gravis [oMG] or gMG); time to gMG, if initial clinical presentation was oMG; maximum MGFA classification since diagnosis; ventilatory support since diagnosis; dates of MG exacerbation or crisis since diagnosis and prior to Day 1; and any MG-related hospitalizations within 2 years prior to the Screening Visit. Myasthenia gravis-specific medication or therapy taken within 2 years prior to the Screening Visit should also be recorded.

### 8.11.5. MGFA Classification

The MGFA Clinical Classification, a universally accepted grading system for patients with MG, will be also used to determine participant eligibility. This system was developed to identify subgroups that share distinct clinical features or disease severity that may necessitate different prognoses or responses to treatment (Jaretzki, 2000).
Class I	Any ocular muscle weakness; may have weakness of eye closure. All other muscle strength is normal.	
Class II	Mild weakness affecting other than ocular muscles; may also have ocular muscle weakness of any severity.	
Class IIa	
 
Predominantly affecting limb, axial muscles, or both. May also have lesser involvement of oropharyngeal muscles.
 
	
Class IIb	b Predominantly affecting oropharyngeal, respiratory muscles, or both. May also have lesser or equal involvement of limb, axial muscles, or both.	
Class III	Moderate weakness affecting other than ocular muscle; may also have ocular muscle weakness of any severity.	
Class IIIa	Predominantly affecting limb, axial muscles, or both. May also have lesser involvement of oropharyngeal muscles.	
Class IIIb	Predominantly affecting oropharyngeal, respiratory muscles, or both. May also have lesser or equal involvement of limb, axial muscles, or both.	
Class IV	Severe weakness affecting other than ocular muscles; may also have ocular muscle weakness of any severity.	
Class IVa	Predominantly affecting limb and/or axial muscles. May also have lesser involvement of oropharyngeal muscles.	
Class IVb	Class IVb Predominantly affecting oropharyngeal, respiratory muscles, or both. May also have lesser or equal involvement of limb, axial muscles, or both.	
Class V	Defined by intubation, with or without mechanical ventilation, except when employed during routine postoperative management. Use of a feeding tube without intubation places the patient in Class IVb.	
C	00	

Table 10:	MGFA	Classification	System
-----------	------	----------------	--------

Source: Jaretzki, 2000

